CONFIDENTIAL AND PROPRIETARY

Information provided herein is the property of the University-Hospital of Brescia. Nothing herein is to be reproduced, published, or disclosed to others in any way without the prior expressed written permission of the University-Hospital of Brescia.

Title of Study: The role of a new prosthodontics device in hard and soft tissue changing after subcrestal implant placement: 12 months parallel randomized clinical trial.

Type of Study: Clinical

Protocol No: PROTOCOL NABUT2020

Expected study start date: September, 2020 (study initiation)

Study Location/Country: Brescia, Italy

Study Originator(s)/ Contact (name, phone, fax): [name], [name], [contact], email: [contact]

Test Products w/ PDM Numbers:

CE marked Medical Device to be used as a prosthodontics device after subcrestal implant placement in patients with monoedentulia (Confidential information).

Study Title:	The role of a new prosthodontics device in hard and soft tissue changing after subcrestal implant placement: 12 months parallel randomized clinical trial.
Study sites:	[name] (lead site) University-Hospital of Brescia Brescia, Italy.
Study Phase:	IV.
Name of Medical Device:	GFA® Gingival Former Abutment (Advan S.r.l. [name])
Objective:	The objective of the clinical study is to assess the efficacy of a new prosthodontics device (GFA) in hard and soft tissue changing after subcrestal implant placement.
Patient Population:	40 patients, systemically healthy, male and female adults (18 – 75 years), with posterior monoedentulia at least 5 months.
Structure:	Parallel arms: Number of treatments: 1 (test group: subcrestal implant placement and GFA; control group: crestal implant placement and healing abutment).
	Duration of study: 27 months.
Number of Centers:	One.
Blinding:	Statistician
Method of Patient Selection:	Posterior monoedentulia intercalated with 11mm of residual bone
Total Sample Size:	40 adult subjects will be recruited (randomized) to participate in this study, with 34 expected to complete the study.
Primary Efficacy Variable:	Primary outcome measure will be the changing of radiographically MBL (marginal bone level) around implant.

**The role of a new prosthodontics device in hard and soft tissue changing after
subcrestal implant placement: 12 months parallel randomized clinical trial.
PROTOCOL #NABUT 2020**

Protocol Date: March 16, 2020

Protocol Approval

Signature Page

[name]
University-Hospital of Brescia, Italy

Date

ADDRESSES AND RESPONSIBILITIES

Addresses

Study Centres:

Section of Periodontics, School of Dentistry, Department of
Surgical Specialities, Radiological Science and Public Health
University of Brescia
[name]
[name]

[name] (Principal Investigator)
[contact]
Email: [contact]

Study coordinator:

[name]
Section of Periodontics, School of Dentistry, Department of
Surgical Specialities, Radiological Science and Public Health
University-Hospital of Brescia
Brescia, IT

Data Management & Monitoring:

[name]
Section of Periodontics, School of Dentistry, Department of
Surgical Specialities, Radiological Science and Public Health
University-Hospital of Brescia
Brescia, IT

Statistician:

[name]
Unit of Biostatistics and Bioinformatics,
Department of Molecular and Translational Medicine
University of Brescia
Brescia, IT

Responsibilities

The **principal investigator's** responsibilities are described in detail in ISO norm 14155:2011 for the clinical investigation of medical devices for human subjects.

The role of the principal investigator is to implement and manage the day-to-day conduct of the clinical investigation as well as ensure data integrity and the rights, safety and well-being of the subjects involved in the clinical investigation.

The principal investigator shall be qualified by education, training and experience to assume responsibilities for the proper conduct of the clinical investigation. In particular, the principal investigator is responsible for:

- qualification of investigation site;
- communication with Ethics Committee;
- compliance with Informed Consent process;
- compliance with Clinical Investigation Plan.

Under the direct supervision of the Principal Investigator, certain duties may be delegated during the course of the study. These responsibilities will be documented on the transfer of responsibilities form maintained in the Investigator Site file.

The **Statistician** will be responsible for:

- sample size calculation;
- statistical plan;
- statistical section of the protocol;
- statistical evaluation;
- final statistical report.

OBJECTIVE

The study will be performed to assess the efficacy of a new prosthodontics device (GFA) in hard and soft tissue changing after subcrestal implant placement in terms of MBL and peri-implant tissues health.

INTRODUCTION

At present there is no scientific evidence in dentistry about the origin and treatment of perimplatitis and mucositis. These peri-implant pathologies can be partially prevented through periodontal diagnosis, correct implant placement and prosthetic loading.

In the literature, there is a physiological bone loss around implant after the placement (1 mm the first year and 0.2 mm each subsequent year). Different types of implants have been designed (laserization of the collar, platform switching..) to try to control this phenomenon with discordant results. Different surgical protocols for implant insertion have been created to minimize bone resorption: a subcrestal implant seems to partially overcome this problem even if this procedure increase the transmucosal tunnel: growing the risk of peri-implant soft tissue infection.

Tissue healing around the implants is not comparable to the natural dental element: the risk of inflammation and consequently of infection is higher around the implants because there is no stable seal between the two structures (tissue and implant).

The prosthetic structure of the GFA was created to overcome these problems: crestal bone reabsorption and transmucosal tunnel. Our objective is to validate or deny this claim.

STUDY OUTCOMES

- a. Primary outcome measure: radiographically change in MBL
- b. Secondary outcomes changes in the following clinical parameters:
 - PD (Probing Depth),
 - REC (Clinical Gingival Recession),
 - BOP (Bleeding on Probing),
 - PI (Plaque Index).

STUDY POPULATION

Forty (40) adults, aged 18-75 years, will be entered into study (randomized). It is expected that forty (34) subjects will complete the study.

Randomized subjects who deviate from the protocol (major protocol deviation) and, for this reason, are excluded from the analysis, will be replaced to guarantee that the sample required for the analysis (34) is reached.

Patients will be treated at the Department of Surgical Specialties Radiological Science and Public Health, School of Dentistry, Section of Periodontics, Brescia, Italy from 09/2020.

Inclusion Characteristics

- Comprehension and signed Informed Consent Form.
- Male and female subjects, aged 18-75 years, inclusive.
- Good general health (free of systemic diseases such as diabetes, HIV infection or genetic disorder, ongoing malignant disease of any type that could influence the outcome of the treatment and might interfere with the evaluation of the study objectives).
- Good oral health (no decay, periapical or periodontal lesions, PI and BOP < 25%).
- Patient with posterior monoedentulia:
 - at least 5 months,
 - mandibular or maxillary,
 - intercalated (distance between teeth more than 7.5 mm),
 - at least 11 mm of height residual bone (from bone crest to maxillary sinus or inferior alveolar nerve),
 - at least 5 mm of bone width (buccal – palatal/lingual).
- Availability for the 12-month duration of the study for an assigned subject.

Exclusion Characteristics

- Not willing to follow the agreed protocol.
- Presence of orthodontic appliances.
- Smokers more than 10 cigarettes per day.
- Chronic obstructive pulmonary disease and asthma.
- Tumors or significant pathology of the soft or hard tissues of the oral cavity.
- Current radiotherapy or chemotherapy.
- Pregnant or lactating women.
- Parafunctions like bruxism.
- Previous interventions to increase bone thickness in the implant area.
- Current or past assumption of medications that may influence surgical therapy and/or interfere with healing following surgical treatment.
- Systemic diseases that constitute a contraindication to surgical therapy and/or interfere with healing following surgical treatment.

A written informed consent will be obtained from each included patient after explanation of the risks and benefits of participating to this study. No change in the trial design will be made after approval of the Ethical Committee.

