1. STUDY DESIGN

The study design was chosen according to the current standards required by ISO, GCP and according to national requirements.

- a. A Parallel-Arm, Statistician is blinded, RCT will be established;
- b. The RCT will be run as mono-center;
- c. A total of 40 subjects will be recruited to participate in the study. It is expected that all of 34 subjects will complete the study in total;
- d. Admission into the study will be via rolling admission (estimated recruitment time: 12 months);
- e. Each subject must have posterior monoedentulia (mandibular or maxillary) intercalated;
- f. Each subject will follow the following treatment protocol:
 1. Visit 1: (Screening)
 - a. Screening and entry into study.
 - b. Verification of the eligibility of each subject by performing intraoral radiography.
 - c. Explanation of the research protocol.
 - d. Consent secured.
 - e. Delivery of the medical request for CBCT (cone beam computed tomography) and for the antibiotic (Amoxicillin 1000mg 2cp/die every 12 hours for 6 days or Azithromycin 500mg 1cp/die every 24 hours for 6 days).
 2. When CBCT is ready the patient have to give it to the Principal Investigator to confirm the eligibility of each subject and to plan the surgery. Professional dental hygiene session is performed before surgery.
 3. Visit 2: (Treatment)
 - a. Assessment of antibiotic prophylaxis, locoregional anesthesia and opening of a thickness flap limited to the intervention area.
 - b. According to the list of randomization the patient will be allocated into one of the two arm of surgical treatment. Group A (control group): placement of the endosseous crestal implant through dedicated drills with 35N insertion torque and healing abutment. Group B (test group): placement of the endosseous subcrestal implant (2 mm under crestal bone) through dedicated drills with 35N insertion

torque and GFA (Gingival Former Abutment). Both group receive the same implant: TZero® (L= 9 mm, Ø 3,6 mm or L= 7,5 mm, Ø 4,3 mm) (Advan S.r.l. [name])

- c. Suture.
- d. Execution of intra-oral and post-operative X-Rays.

After 7 days of the surgery suture removal.

- 4. Visit 3: (after 3 months from visit 2) (Treatment)
 - a. Periodontal charting around the healing abutment or GFA (PD, BOP, PI) with calibrated periodontal probe.
 - b. Impression taking for prosthetic finalization.
- 5. Visit 4: (after a week from Visit 3: Baseline – T0): (Treatment)

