 - a. Prosthetic finalization and loading.
 - b. Periodontal charting around the new prosthetic crown (PD, BOP, PI, REC).
 - c. Take a standardized x- Ray (Bite Block).
- 6. Visit 5 (6 months from baseline – T1): (Follow-up)
 - a. Control.
 - b. Periodontal charting around the prosthetic crown (PD, BOP, PI, REC).
 - c. Take a standardized x- Ray (Bite Block).
 - d. Professional dental hygiene session.
- 7. Visit 6 (12 months from baseline – T2):
 - a. Control.
 - b. Periodontal charting around the prosthetic crown (PD, BOP, PI ,REC).
 - c. Take a standardized x- Ray (Bite Block).
 - d. Professional dental hygiene session.
- g. All treatments are made by the same clinician;
- h. Data collection:
 - Standardized X- Ray: control periapical radiographs is performed using a long-cone paralleling technique and an individual X-ray holder (bite block) to ensure reproducibility. Built thanks to impression material.
 - A calibrated periodontal probe (Click-Probe™ Kerr Dental) is used on six sites per tooth (mesio-buccal, buccal, disto-buccal, mesio-lingual, lingual and disto-lingual) with a standard probing force by the same clinician. Measurements are rounded to the nearest millimeter;

- j. Clinical and radiographical assessment data will be recorded via hard copy CRFs. CRFs will be submitted to a data entry staff member for entry into the statistical database. At the conclusion of the study, such statistical database will be submitted to the statistician for the preparation of the statistical analysis and the final study report.
- k. Prosthetic finalization is given to the dental laboratory.

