2. TREATMENTS

Implant kit, implants and every component will be delivered to the study center prior study start by Advan S.r.l. [name]:

- Surgical Kit PRO: GKC13
- Set countersink GFA: GKM10
- Kit stop drills: GST11
- Implant: TZero - T3609 (D3,6 L9,0) - T4307 (D4,3 L7,5)
- GFA: 04GFX03 (D4,0 H3,5) - 04GFX04 (D4,0 H4,5) - 04GFX05 (D4,0 H5,5)
- component GFA: 01GFT01 (healing stopper H1) - 01GFT03 (healing stopper H3) -01GFT05 (healing stopper H5) - 01TGF10 (transfer pick-up) - 01AGF10 (analogo GFA) -01CGF40 (moncone calcinabile con base in cobalto-cromo)
- for control group: 05OMG12 (healing abutment H2) - 05OMG13 (healing abutment H3) - 05OMG14 (healing abutment H4) - 01OTR10 (transfer pick-up) - 41CCN40 (moncone calcinabile con base in cobalto-cromo)

Radiographically Analysis

Specification of software analysis

Peri-apical x-ray examinations will be performed using phosphor image plates (FONA™ Dental Image Plates) and then acquired through a digital scanner device (FONA ScaNeo™).

All radiographical images will be later analyzed by the same external examiner, which will measure marginal bone level parameter (MBL) around placed endosseous implants using an image analysis software (ImageJ™).

In particular bone levels will be determined, both mesially and distally the dental implant, using the “Measure” function of the software, which records the distance between the most apical bone point and the most coronal bone point in 0.3 mm range from the implant.

Measurements will be all recorded to allow the observation of bone level changes over time.

Concomitant Therapy

A necessary concomitant medication or therapy is permitted as long as it is not excluded in the exclusion criteria. Every medication has to be reported in the CRF (Appendix 1) and in the Concomitant Medication form (Appendix 2). All changes during the study are to be reported in the CRF. Usage of prohibited therapy will lead to the exclusion of the subject.

Blinding and Randomization

Blinding:

The statistician and the patient will be blinded to the group identification. The operator will know the treatment allocation. Knowledge of the randomization list will be limited to the persons responsible for creation of the randomization list, provider of randomization numbers to study site, and delivery of the test/control treatment until the last subject (i.e. final examination of the last subject), quality control and verification of the CRFs is completed.

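### Soft-tissue outcomes are defined only as changes, so a lasting probing-depth difference created at surgery would cancel out of the comparison meant to test the transmucosal-tunnel claim

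*Combined protocol and SAP*

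**What the plan says.** The Introduction states that with a subcrestal implant "this procedure increase the transmucosal tunnel: growing the risk of peri-implant soft tissue infection". It continues: "The prosthetic structure of the GFA was created to overcome these problems: crestal bone reabsorption and transmucosal tunnel", and gives the trial's aim as confirming or refuting that. The Objective names peri-implant tissue health next to marginal bone level (MBL).

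Study Outcomes words the soft-tissue endpoints as "Secondary outcomes changes in the following clinical parameters": PD, REC, BOP and PI. It does not give the starting point of the change, but Study Design labels Visit 4 as baseline (T0).

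The arms separate at Visit 2, where the test arm has "placement of the endosseous subcrestal implant (2 mm under crestal bone" and the control implant is placed at the crest. PD, BOP and PI are charted three months later at Visit 3, around the healing abutment or GFA. At Visit 4, one week after that, the plan lists "Periodontal charting around the new prosthetic crown (PD, BOP, PI, REC". Charting is repeated at 6 months (T1) and 12 months (T2).

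Section 4, Statistical Analysis, assigns the secondary outcomes to GEE, with a Gaussian error for PPD, CAL and REC and a binomial error for BOP. It does not say whether the response is a visit value or a change. It names no arm, visit or interaction term, no contrast and no handling of baseline.

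**The concern.** The tunnel claim is at least partly a question of level: once healed and loaded, is the pocket around the test implant deeper than the one around the control? An outcome defined as change answers a different question, namely whether the arms move apart after T0. If the extra depth arises at surgery and persists, the two answers diverge.

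For PD no better starting value exists. There is no implant pocket before surgery, so every peri-implant baseline already contains the treatment effect. A report of no difference in PD change could then be read as support for the device even if test pockets were deeper throughout. The possible error favours the device and affects the soft-tissue half of the objective.

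**Working it through.** **The plan's own figure.** Section 4 gives a difference of 0.5 mm, SD 0.5 mm, 5% significance, at least 80% power and balanced groups, for MBL. The standardised difference is 0.5/0.5 = 1. A two-sided t-test (sidedness is assumed) needs 16.71 per arm, so 17 per arm or 34 in total. Power is 80.7% with 17 per arm and 78.1% with 16. With 15% drop-out, 34/0.85 = 40. The figure reproduces. It does not bear on the concern except to supply 17 per arm for what follows.

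**Which PD readings could serve as a start.**
- Visit 1: marked for PD, REC, BOP and PI in the flow chart, but no implant is present, so there is no peri-implant PD.
- Visit 3: after surgery; PD, BOP and PI only, and not marked in the flow chart's clinical data row.
- Visit 4 (T0): after surgery; first charting around the crown.

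**Algebra.** Let the control means be m0 at T0 and m2 at T2, and let the test arm be deeper by d0 and d2.
- Change contrast: [(m2 + d2) − (m0 + d0)] − (m2 − m0) = d2 − d0.
- T2 level contrast: (m2 + d2) − m2 = d2.

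If d0 = d2 = d, the change contrast is 0 for any d. If the penalty grows from 1.0 to 1.5 mm, the change contrast shows 0.5 of the 1.5 mm. If it shrinks from 1.0 to 0.5 mm, the change contrast is −0.5 mm, an apparent advantage for the test arm while its pocket is still 0.5 mm deeper. These millimetre values are illustrations.

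**Size under assumptions.** The documents give no PD offset, SD or T0–T2 correlation. With a constant 1.0 mm penalty, 17 per arm, SD 0.5 or 1.0 mm and correlation 0.3, 0.5 or 0.7, simulation (20,000 runs) gave a mean difference in change of 0.00 mm and rejection rates of 4.7% to 5.1%, which is the false-positive rate. The T2 level contrast recovered 1.0 mm. Its power by t-test is:

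| Constant PD penalty | SD 0.5 mm | SD 0.75 mm | SD 1.0 mm |
|---|---|---|---|
| 0.5 mm | 80.7% | 47.0% | 29.3% |
| 1.0 mm | >99% | 96.5% | 80.7% |

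**Adjusting for T0 PD.** With equal SDs at T0 and T2, the adjusted arm effect is d(1 − r), where r is the T0–T2 correlation. For d = 1.0 mm this is 0.70, 0.50 and 0.30 mm at r = 0.3, 0.5 and 0.7, and simulation agreed. Treating T0 as a pre-treatment covariate thus removes part of the penalty.

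**Precision.** The variance of a change is 2·SD²·(1 − r), against SD² for a level. Levels are the less precise of the two only if r exceeds 0.5. At r = 0.7 the level interval is 1/√0.6 = 1.29 times as wide.

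**The case against.** The strongest reply is that the analysis may use levels anyway. GEE is normally fitted to repeated visit values, and a binomial error for BOP suits bleeding present or absent at a site, not a change. Descriptive statistics are also planned, so deeper test pockets might be visible in the tables. This has force for BOP, and it means that a change-score analysis of PD is not established. A reader might infer that the trial is bound to hide a tunnel penalty and vindicate the device; the documents do not support that. But Section 4 names no response or contrast for PD. It lists CAL, which is not a defined outcome, and omits PI. It does not say that descriptive statistics will be shown by arm and visit. A level analysis of PD would also depart from the outcome definition. So the section leaves the gap open.

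A second reply is that the Introduction ties the tunnel to infection risk, and inflammation or deepening that develops after T0 does show as change. That is correct. A T2 level alone could not separate a fixed anatomical offset from later deterioration. Changes should therefore stay, with levels added.

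**Conclusion.** The point holds for PD: as defined, the outcome cannot show a between-arm difference that arises at surgery and stays constant. Exact cancellation depends on that constancy; a growing or shrinking penalty appears in part. For peri-implant BOP the point is weaker. The size of any PD penalty is unknown and could be zero. These are secondary outcomes, and the primary outcome and sample size are unaffected.

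Three stronger readings are tempting but unsupported.
- **A penalty of 1.5 mm.** Section 2 lists "GFA: 04GFX03 (D4,0 H3,5) - 04GFX04 (D4,0 H4,5) - 04GFX05 (D4,0 H5,5") and "05OMG12 (healing abutment H2) - 05OMG13 (healing abutment H3) - 05OMG14 (healing abutment H4"), which differ by 1.5 mm if paired in order. Nothing in the plan pairs them or says where height is measured from. If it is measured from the implant platform, a 3.5 mm GFA set 2 mm below the crest rises 3.5 − 2 = 1.5 mm above it, against 2 mm for the shortest healing abutment at the crest. That is 0.5 mm less, so the sign could reverse.
- **The same fault in PI.** Section 3 describes PI as a full-mouth score and the flow chart marks it at Visit 1, so a pre-surgical value may exist. Plaque also does not measure tunnel length.
- **Bleeding at T0 distorted by component handling that differs by arm.** Section 2 lists a transfer and a coping for the control arm too, and nothing says that either arm is handled less at Visit 4.

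**What to change.** In Study Outcomes, keep the changes and add the between-arm difference in PD and in peri-implant BOP levels at T2, with T0 and T1 levels also compared. State that the tunnel claim is judged on these levels together with later change.

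In Section 4, state that the GEE is fitted to the visit values with arm, visit and arm-by-visit terms. The arm contrast at T2 then gives the level difference, and the arm-by-visit term from T0 to T2 gives the difference in change, so one model supplies both. State that T0 PD will not be adjusted for as if it were a pre-treatment covariate.

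The cost is wording only: all values are already charted, and no visit, measurement or patient is added. The downsides are a few more secondary contrasts and possibly wider intervals for levels than for changes. For a small penalty with a large SD, power is low (29.3% for 0.5 mm at SD 1.0 mm), so a non-significant level difference should be reported with its interval and not read as absence of a penalty.

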4. STATISTICAL ANALYSIS

Sample size determination

Sample size was compute assuming a two parallel groups design with balanced groups and an independent sample t-test. We assumed a single implant and a single measurement for patient, a standard deviation of 0.5 mm and an average difference of at least 0.5mm. A total sample size of 34 patients will provide a power of at least 80% at a 5% significance level. Assuming a 15% drop-out , the total sample size will be N=40 patients.

Statistical Analysis

Data will be described using standard statistics such as, mean, median standard deviation and IQR for quantitative variable, and counts and percentages for qualitative variables.

Variation in MBL will be modelled using both a simple t-test for independent samples (after averaging values within patients) as well as a multilevel model using GEE (Generalised Estimating Equations) on individual site measurements and accounting for within subject correlation.

Secondary continuous outcomes will be modelled using GEE with ad hoc error distribution according to outcome (Gaussian for PPD, CAL, REC, binomial for BOP).

Results will be expressed as estimates and relative 95% confidence intervals. A significant level of 5% will be used for all the comparisons and all analysis will be performed using R (version 3.6.3 or higher).

Evaluation of Safety

The following safety variables will be used for the evaluation of safety:

- Adverse events (AE);
- Adverse reactions (AR).

The total number of AEs and the total number of AEs at least possibly related to the study treatment, as well as the total number of patients affected by at least one adverse event will be calculated per treatment group.

The type of AE classified by organ system (according to MedDRA terminology) will be tabulated. Serious and/or unanticipated adverse events and AEs resulting in discontinuation or reduction/withdrawal of the study treatment will be presented separately.

Safety analysis set

Safety summaries will be based on the safety analysis set which will consist of all patients who received the test/control treatment.

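### Randomised patients with an undefined major protocol deviation can be dropped from the analysis and replaced, and no MBL analysis by assigned arm is planned, so the primary comparison is open to selection bias

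*Combined protocol and SAP*

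**What the plan says.** The Study Population section of the protocol provides: "Randomized subjects who deviate from the protocol (major protocol deviation) and, for this reason, are excluded from the analysis, will be replaced". The stated purpose is to secure the 34 patients needed for analysis. No section defines a major deviation, lists qualifying events or says who classifies them.

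Two other sections give related triggers, but neither is offered as the definition. Section 2 (Concomitant Therapy) says "Usage of prohibited therapy will lead to the exclusion of the subject". Section 6 allows withdrawal of a subject who does not substantially comply.

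For the primary outcome, Section 4 says "Variation in MBL will be modelled using both a simple t-test for independent samples (after averaging values within patients", together with a GEE model on site measurements. It names no population for either analysis. The only set defined is for safety: "Safety summaries will be based on the safety analysis set which will consist of all patients who received the test/control treatment".

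On masking, Section 2 says "The statistician and the patient will be blinded to the group identification" and "The operator will know the treatment allocation". It also restricts knowledge of the randomisation list to those who create it, supply the numbers or deliver treatment, until the last subject's final examination and verification of the CRFs are completed. On measurement it says "All radiographical images will be later analyzed by the same external examiner". Section 5 has the principal investigator check CRFs for compliance during the study. Section 7 plans a blind data review by investigator and statistician after the study ends and before analysis.

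**The concern.** Randomisation makes the two arms comparable at the point of allocation. Removing patients later, for reasons that may depend on both the arm and how the implant site is faring, can undo that. Here the provision for removal is written down and the criterion is open. No text requires the decision to be made without arm labels.

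The larger problem is that nothing is planned to set beside the result. If the patients analysed differ from those randomised, the plan has no MBL comparison by assigned arm, even as a sensitivity analysis, from which a reader could judge whether the exclusions mattered. Patients dropped from follow-up may also have no 12-month film, and that cannot be recovered later.

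**Working it through.** **1. The plan's own sample size.** Inputs from Section 4: difference 0.5 mm, SD 0.5 mm, 5% significance, power at least 80%, balanced arms, t-test. Two-sided testing is assumed because sidedness is not stated.
- Standardised effect: 0.5 / 0.5 = 1.0.
- The noncentral-t calculation gives 16.71 per arm, rounded up to 17, so 34 in total. Power at 17 per arm is 80.7%.
- For loss, the plan says "Assuming a 15% drop-out , the total sample size will be N=40 patients": 34 / 0.85 = 40.

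Both figures reproduce. The 40 already allow for 40 − 34 = 6 losses, so replacement matters for power only beyond that.

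**2. How exclusion could bias the comparison (illustration).** Assumptions, none taken from the documents except the SD and the 20 per arm: normal data, SD 0.5 mm, no true effect, equal numbers excluded per arm. Exclusion is random in the control arm and related to bone loss in the test arm with correlation r. Replacement is read as adding only as many patients as are needed to reach 34. There were 200,000 simulated trials per scenario, analysed by pooled t-test at two-sided 5%. A false claim is a significant result favouring test; its nominal rate is 2.5%.

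| Excluded per arm | Replaced per arm | Bias favouring test, mm (r = 0.3 / 0.5 / 1.0) | False claims for test (r = 0.3 / 0.5 / 1.0) |
|---|---|---|---|
| 1 | 0 | 0.015 / 0.025 / 0.049 | 3.1% / 3.6% / 5.4% |
| 3 | 0 (34 remain) | 0.039 / 0.065 / 0.130 | 4.2% / 5.9% / 13.8% |
| 4 | 1 (back to 34) | 0.047 / 0.079 / 0.157 | 4.6% / 6.8% / 17.6% |

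The bias is proportional to r: with three excluded, 0.130 × 0.3 = 0.039 and 0.130 × 0.5 = 0.065. Against the 0.5 mm target these are 0.039 / 0.5 = 7.8%, 0.065 / 0.5 = 13% and 0.130 / 0.5 = 26%.

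Two checks fix the limits. With r = 0, three excluded per arm gives a bias of 0.000 mm. With the same outcome-related mechanism in both arms, the bias is within 0.001 mm of zero.

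The third row shows that topping up the numbers does not remove the bias, which comes from the exclusion.

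**3. What the change does to power.** For 0.5 mm and SD 0.5 mm, power is 86.9% at 20 per arm, 80.7% at 17 and 78.1% at 16. If m of 20 test patients are retained deviators with no benefit, the expected difference is 0.5 × (20 − m) / 20. For m = 1 / 2 / 3 this is 0.475 / 0.450 / 0.425 mm. Power with all 40 analysed is then about 83.3% / 79.2% / 74.5%, holding the SD at 0.5 mm.

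**The case against.** The strongest reply is that the protocol already limits the opportunity for selection. An external examiner reads the films later, so whoever judges a deviation need not have the MBL value. Knowledge of the randomisation list is restricted until the last examination and CRF verification. A blind data review precedes analysis, and Section 10 requires the final report to describe deviations and withdrawals.

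This has weight: it makes direct selection on the MBL reading unlikely, and r = 1.0 remote. It does not settle the matter. Exclusion could still follow correlates of outcome, such as poor compliance or visible complications. The restriction on the list exempts those delivering treatment, and CRF entries may reveal the arm. The blind review is not given the task of classifying deviations, and it comes too late for replacement decisions. A list of deviations is not a comparison by assigned arm.

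It is also fair to say that the illustrated harm is small at modest correlation, and that no text suggests outcome-related exclusion in the test arm alone.

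A reader might infer three stronger things that the documents do not support:
- **That the operator decides who is excluded.** No section says so. Compliance checking is given to the principal investigator, and nothing in the available text says that the principal investigator is the operator.
- **That every major deviator must be excluded.** The sentence presupposes exclusion and provides for replacement; it does not strictly command exclusion in each case. Equally, no other text keeps deviators in the MBL analysis.
- **That replacement causes the bias.** It does not. Replacement bears on power and on the fixed total of 40.

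**Conclusion.** The point stands as a stated provision that leaves the primary comparison open to selection bias. It rests on three facts in the text: provision for post-randomisation exclusion, no definition of the criterion, and no planned MBL analysis by assigned arm. It does not rest on the simulated figures, which show only what could happen under assumed exclusion related to outcome in the test arm alone.

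A reader might take those figures to mean that the trial will favour the test device. The documents do not support that. Direction and size are unknown, and the bias is zero if exclusions are unrelated to outcome. With no true effect, it is also zero if the same mechanism acts in both arms. The sample size is not in dispute.

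Because the point affects the primary outcome and lost 12-month films cannot be recovered, the wording should be changed before patients are dropped and, at the latest, before database lock.

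**What to change.** 1. **Primary analysis.** Amend Study Population and Section 4 so that the MBL t-test and GEE include every randomised patient with the needed films, in the arm assigned and regardless of protocol deviation. T0 and T2 are assumed here from the 12-month title, because Section 4 names no time point; the plan should name it. Call this an available-case analysis by assigned arm. It cannot cover everyone randomised, since allocation is at Visit 2 and T0 comes three months and one week later. Keep collecting films at scheduled visits where consent and the protocol's withdrawal rules (Sections 6, 8 and 11) allow. Reconcile the exclusion in Section 2 and the withdrawal in Section 6 with this by stating whether each means leaving treatment, follow-up or the analysis.

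2. **Missing films.** Report patients without a T0 or T2 film by arm and reason. Add a sensitivity analysis over all randomised patients: multiple imputation of the change within arm, a stated range of shifts applied to the imputed test-arm values, variance combined across imputations, and a report of where the conclusion changes. With 3 of 20 test values missing, shifts of 0.5 and 1.0 mm move the arm difference by 3/20 × 0.5 = 0.075 mm and 3/20 × 1.0 = 0.150 mm. Single imputation should not be used: with 3 of 20 missing at random per arm and no true effect, it gives roughly 9 to 10% two-sided error in simulation.

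3. **Deviations.** List major deviations in advance and classify them without arm labels before database lock; the Section 7 review could take this on. Use them only for a per-protocol sensitivity analysis.

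4. **Optional.** Drop the replacement rule, since 40 already allows 15% loss. This concerns power and the fixed total, not the selection bias.

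**Cost.** Amended wording by the route in Section 9, with no added patients and no visits beyond the flow chart, although deviators who would have been dropped would attend T1 and T2. There are two downsides. Retained deviators may dilute the effect, as shown in the power figures above. If replacement is also dropped, 34 analysed patients are no longer guaranteed, and at 16 per arm power falls just below the 80% target.
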